Clinical Trial design:	This is a randomized, placebo-controlled, double-blind, parallel-group, dose-ranging study. Eligible subjects will be randomized (1:1:1:1) to receive subcutaneous injection of various doses of nemolizumab or its placebo every 4 weeks, in addition to background TCS therapy. Randomization will be stratified by AD severity (Investigator's Global Assessment [IGA] 3 or 4). 
  
 Group	Dose on day 1	Dose at weeks 4, 8, 12, 16 & 20	
   
 1	20 mg	10 mg	
 
 2	60 mg	30 mg	
 
 3	90 mg	90 mg	
 
 4	placebo	placebo	
  
	Group	Dose on day 1	Dose at weeks 4, 8, 12, 16 & 20	1	20 mg	10 mg	2	60 mg	30 mg	3	90 mg	90 mg	4	placebo	placebo
Group	Dose on day 1	Dose at weeks 4, 8, 12, 16 & 20														
1	20 mg	10 mg														
2	60 mg	30 mg														
3	90 mg	90 mg														
4	placebo	placebo														
Total number of subjects (Planned):	Approximately 250 subjects will be screened to result in 200 randomized subjects (50 subjects per group).															
Number of clinical trial centers (Planned):	Approximately 70 sites															
Region(s) involved (Planned):	Europe/North America/Asia-Pacific															
Clinical trial duration:	The planned duration of this clinical trial (from First Subject In [FSI] to Last Subject Out [LSO]) is approximately 15 months, with approximately 6 months of recruitment (from FSI to Last Subject In [LSI]).															
Duration of subject participation:	Each subject will participate in the clinical trial for up to 36 weeks, with a 2 to 4-week run-in period, a 24-week treatment period (with the last drug injection at week 20), and an 8-week follow-up period (12 weeks after the last study drug injection).															

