3 OVERALL CLINICAL TRIAL DESCRIPTION

3.1 Overview

This is a randomized, placebo-controlled, double-blind, parallel-group, dose-ranging study to evaluate the efficacy and safety of various doses of nemolizumab in moderate-to-severe AD subjects with severe pruritus. The duration of this clinical trial is up to 36 weeks for a given subject, including a 2 to 4-week run-in period, a 24-week treatment period and an 8-week follow-up period (12 weeks after the last study drug administration).

Eligible subjects must have moderate-to-severe AD, severe pruritus and a documented history of inadequate response to topical AD medications. Subjects meeting the inclusion/exclusion criteria at the screening visit will receive background therapy of AD (including a moisturizer, a medium potency TCS for the body, and a low potency TCS for the face, neck etc.) to be used throughout the study. One retest is allowed for the tests of tuberculosis (TB) and CPK. Subjects who still meet the inclusion/exclusion criteria at the baseline visit will be randomized in a 1:1:1:1 ratio to either of the 3 groups of nemolizumab or placebo. Injection of study drug will occur every 4 weeks (at weeks 4, 8, 12, 16 & 20), and a loading dose will be administered on day 1 for the groups of 10mg and 30mg only (20mg and 60mg, respectively). For 90mg group, the same dose will be administered at each injection visit. Randomization will be stratified by AD severity based on the baseline IGA score (3 or 4).

Group	Dose on day 1	Dose at weeks 4, 8, 12, 16 & 20
1	20 mg	10 mg
2	60 mg	30 mg
3	90 mg	90 mg
4	placebo	placebo

The schedule of assessments is summarized in [Table 2](#). Assessments of efficacy, safety and PK will be conducted throughout this clinical trial. Subjects will evaluate the severity of their pruritus daily. The last study drug injection will occur at week 20, and the end of treatment visit will occur at week 24, when the primary endpoint assessment will be conducted. The end of study visit will occur at week 32, 8 weeks after the end-of-treatment visit and 12 weeks after the last study drug administration.

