6.1.8.2 Study drug discontinuation

The study drug must be permanently discontinued when any of the following conditions is reported for a subject during the clinical trial:

- Serious immediate-type allergic manifestations including anaphylactic reaction
- Diagnosis of a malignancy (except curatively treated in situ cervical carcinoma or basal cell carcinoma)
- Pregnancy
- Any opportunistic infection (such as active TB and other infections whose nature or course suggest an immune-compromised status)
- Systemic rescue therapy (such as cyclosporine, systemic corticosteroids, methotrexate, mycophenolate mofetil, azathioprine or biologics) or TCI used in body areas other than the face, neck, or genital areas
- Asthma /worsening of asthma reported as a serious adverse event

In the event that the study drug is discontinued, the subjects should remain in the study and will be asked to return for all remaining visits and all assessments (including daily assessments of pruritus and sleep disturbance) according to, except those who withdraw their consent for study participation.

In the event of a missed dose (i.e. temporary discontinuation of the study drug), it will be documented in the eCRF that the drug has not been administered at the study visit, together with the reason (e.g. for safety reason). Subjects will be asked to return to the investigational sites for all remaining visits and complete all study assessments and procedures as described in [Table 2](#).

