4.3 Study Subjects

4.3.1 Disposition of Subjects

A clear accounting of the disposition of all subjects who enter the study will be provided, from screening to study completion.

The following subject disposition summaries will be produced:

- The number of subjects screened (Analysis population: All Subjects)
- Subjects Randomized by clinical site and overall (Analysis population: Screened Subjects)
- Screen failures (Analysis population: Screened Subjects)

The following summary will be produced for ITT population.

- The number of subjects randomized
- The number and percentage of subjects treated (with at least one dose of study drug)
- The number and percentage of subjects randomized but not treated (not taken any dose of study drug)
- The number and percentage of subjects who temporarily discontinued the study treatment and reasons for discontinuation
- The number and percentage of subjects who permanently discontinued the study treatment and reason of discontinuation
- The number of subjects completing study treatment (defined as completing week 24 visit)
- The number of subjects completing the study
- The number of subjects who discontinued from the study and reason of discontinuation
- A Kaplan-Meier plot of the time to permanent study treatment discontinuation will be provided. Subjects who did not discontinue from the study drug will be censored at their last dose of study drug (Analysis population: ITT).
- A Kaplan-Meier plot of the time to study discontinuation will be provided. Subjects who did not discontinue from the study will be censored at the date of study completion or the last visit date on the study (Analysis population: ITT).
- Time (days) to permanent discontinuation of study drug by reasons for discontinuation will be displayed graphically in subjects having permanently discontinued study drug.
- Time (days) to study discontinuation by reasons for discontinuation from study will be displayed graphically in subjects having discontinued study.

By-subject listings of eligibility details, randomization details, visit dates and withdrawal/study completion details (including reason for discontinuation and duration of treatment prior to discontinuation) will be provided.

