4.7.4.8 Time to rescue therapy

Time to rescue therapy (days) from date of randomization will be analyzed using KM and Cox proportional hazard model and displayed graphically when appropriate (Analysis population: ITT). Median event times and two-sided 95% CI for each median will be provided when appropriate. The KM survival curves will be displayed for each treatment group along with p-value for differences (each nemolizumab regimen over placebo) based on the Log-rank test stratified by baseline IGA severity (3, 4).

The estimates of the hazard ratio (HR) comparing each nemolizumab regimen with placebo will be derived using the Cox proportional hazard model for the time to event served as a response variable and treatment group, baseline IGA severity as factors. The HRs (each nemolizumab regimen over placebo), corresponding 95% CIs, and two sided p-values for the HRs will be presented.

Time to rescue therapy will be calculated for treatment period only. Subjects who do not experience the event at any time during the treatment period will be censored at the last evaluation time (up to the end of treatment period).

4.7.4.9 Change from baseline in 5-D itch scale total score at week 2

The endpoint will be analyzed using an analysis of covariance (ANCOVA), with treatment group, baseline IGA severity (3, 4) and baseline 5-D itch scale total score as covariates in the model for ITT population. A 95% CI for the difference between each nemolizumab dose regimen and placebo in LSM means and p-value will be calculated based on contrast test statistics.

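### The Kaplan-Meier plot of treatment discontinuation censors completers at the week 20 dose, four weeks before treatment completion, and can fall to zero if a late stop is dated when it occurs

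*SAP*

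**What the plan says.** SAP 4.3.1 plans, in the ITT population, a Kaplan-Meier plot of time to permanent discontinuation of study treatment. Its censoring rule is: "Subjects who did not discontinue from the study drug will be censored at their last dose of study drug".

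The same list reports "The number of subjects completing study treatment (defined as completing week 24 visit", which puts treatment completion at week 24. The protocol agrees. Section 3.1 says "The last study drug injection will occur at week 20, and the end of treatment visit will occur at week 24", and the synopsis describes "a 24-week treatment period (with the last drug injection at week 20". In the schedule of assessments (SAP Appendix 1) week 20 is day 141 ± 5 and week 24 is day 169 ± 5.

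Permanent discontinuation is not confined to the time before the last injection. Protocol 6.1.8.2 says: "The study drug must be permanently discontinued when any of the following conditions is reported for a subject during the clinical trial".

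Two sibling analyses use a different rule. For the plot of study discontinuation in SAP 4.3.1, "Subjects who did not discontinue from the study will be censored at the date of study completion or the last visit date on the study". For time to rescue, SAP 4.7.4.8 says that subjects without the event "will be censored at the last evaluation time (up to the end of treatment period".

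The SAP does not say which date a permanent discontinuation takes: the day of the stop or the day of the last dose.

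**The concern.** Under this rule every completer leaves the risk set at the week 20 injection, 169 − 141 = 28 days before the point at which the SAP itself calls treatment complete. Anyone recorded as stopping in those four weeks is an event when almost nobody else is still counted as at risk. Because a Kaplan-Meier step is the number of events divided by the number at risk, a single such subject can take a whole arm's curve to zero.

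What is at stake is the credibility of one disposition figure. It could show total loss in an arm whose tabulated discontinuation is a few percent, and it could make arms look different because of one subject.

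**Working it through.** The plan gives no figure for this plot and no discontinuation rate, so there is nothing to reproduce. The check asks what the stated rule does to one arm.

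**Inputs.** 50 subjects per arm (Protocol 5.1). Week 20 dose on day 141 ± 5, so in-window doses fall on days 136 to 146; week 24 visit on day 169 (SAP Appendix 1). Assumed: k = 0, 2 or 5 stops before the week 20 window, one late stop, and 49 − k completers with doses spread evenly over the window.

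**Formula.** S = product over event days of (1 − events / number at risk). Before the late stop, S = (50 − k)/50 = 1.00, 0.96 or 0.90.

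**Completers censored at week 24.** At the late stop 50 − k are at risk, so S = (49 − k)/50 = 0.98, 0.94 or 0.88, whichever day the stop falls on.

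**SAP rule, stop dated day 150 or 160.** All completers were censored by day 146, so one subject is at risk and S is multiplied by 1 − 1/1 = 0.

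**SAP rule, stop dated day 143, inside the dosing window.** At risk 18, 18 or 17: 1.00 × 17/18 = 0.94; 0.96 × 17/18 = 0.91; 0.90 × 16/17 = 0.85.

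**SAP rule, event dated at the week 20 dose, day 141.** At risk 28, 27 or 25: 1.00 × 27/28 = 0.964; 0.96 × 26/27 = 0.924; 0.90 × 24/25 = 0.864. Each is 1.6 points below the week 24 result. If every dose falls exactly on day 141 there is no distortion.

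| Final estimate | k = 0 | k = 2 | k = 5 |
|---|---|---|---|
| Censored at week 24 | 0.98 | 0.94 | 0.88 |
| SAP rule, dated day 150 or 160 | 0.00 | 0.00 | 0.00 |
| SAP rule, dated day 143 | 0.94 | 0.91 | 0.85 |
| SAP rule, dated day 141 | 0.96 | 0.92 | 0.86 |

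**How often an arm's curve would end at zero.** Assume that a proportion r stops by week 24 at constant hazard, that events are dated at the stop, and that week 20 doses are uniform over days 136 to 146. Simulating 20,000 arms of 50 gives 28.6%, 48.5%, 62.2% and 72.0% for r = 5%, 10%, 15% and 20%.

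A closed form confirms this. Counting from day 1, day 146 is 145 elapsed days and day 169 is 168. The chance that one subject stops in between is p = (1 − r)^(145/168) − (1 − r), and the chance of at least one such stop in 50 is 1 − (1 − p)^50. For r = 10%, p = 0.9131 − 0.9000 = 0.0131, giving 48%. For r = 5%, p = 0.0067, giving 29%. For r = 20%, p = 0.0248, giving 72% (71.5% before rounding).

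**The case against.** The strongest reply is that the collapse depends on an event date that the SAP leaves undefined. No injection is due after week 20, so a stop in weeks 20 to 24 is largely a matter of recording. If discontinuation is dated at the last dose, the clock already used for censoring, the collapse disappears and about 2 points of distortion remain. This stands, and it is why the conclusion is conditional. The stop must also fall after the last completer's week 20 dose in that arm. Protocol 8.1.4.2 recognises that visits can occur outside their window, and one completer dosed later than the stop keeps the curve above zero. A reader might infer that any stop after week 20 empties the curve. The day 143 case shows that this is not so when doses are spread over the window.

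Second, the correct figures sit beside the plot. SAP 4.3.1 tabulates the number and percentage who permanently discontinue, with reasons, and the number completing treatment. The plot carries no test. This also stands.

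Third, a reader might infer that the flaw undermines judgement of missing data in the week 24 mixed model. The documents do not support that. Subjects who stop study drug are asked to stay for all remaining visits (Protocol 6.1.8.2 and 8.1.4.1), so stopping drug does not in itself remove EASI data. Missing values arise from leaving the study and from rescue (SAP 4.7.1.3), and the curves for those two events do not have this defect.

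What does not fall away is the inconsistency itself: this plot stops following subjects before the treatment period ends, while its two siblings do not.

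**Conclusion.** The point holds as an internal inconsistency in one censoring rule, with a conditional effect. The collapse to zero needs two things: the event is dated at the stop, and it falls after the last completer's week 20 dose in that arm, about day 146 if all visits are in window. Otherwise the distortion is small, about 2 points with the event dated at day 141 and 3 to 4 points in the day 143 example. The range of 29% to 72% rests on assumed discontinuation rates of 5% to 20%, constant hazard and in-window dosing, none of which comes from the documents.

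The consequence is confined to a descriptive figure that could contradict the discontinuation percentages tabulated next to it. No efficacy or safety inference changes. It is worth correcting because the correction is cheap.

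**What to change.** In SAP 4.3.1, replace the censoring sentence for this plot and add three clarifications:

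- Censor subjects who did not permanently discontinue study drug at their week 24 end-of-treatment visit or, if that visit was missed, at their last visit in the treatment period.
- Define the event date as the recorded date of permanent discontinuation.
- Count subjects who leave the study before week 24 as treatment discontinuations rather than censoring them. This follows from the SAP's own definition of completing treatment.
- State how ITT subjects who were randomized but never dosed are handled. They have no last dose, so the present rule gives them no censoring date.

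The cost is a few sentences in the SAP before unblinding and a small programming change. The plot already needs a discontinuation date for each subject who stops, so no new data should be required.

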4.3.2 Protocol Deviations

Deviations from the protocol including violations of inclusion/exclusion criteria will be assessed as ‘minor’ or ‘major’. Major PDs are defined as those deviations from the protocol that are likely to have an impact on the subject’s right, safety, well-being, and/or the validity of the data for analysis. Minor deviations include all deviations from the protocol excluding those considered as major. The impact of major protocol deviations on the efficacy and/or safety results will be investigated by assessing the robustness of the study results and conclusions to the choice of analysis population (see Section 4.4), both including and excluding data potentially affected by major protocol deviations. Major PDs that will lead to the exclusion of a subject from the per-protocol (PP) population will be identified. The final determination of major protocol deviations and the exclusion of subjects from each of the analysis populations will be made prior to database lock.

Major PDs that could potentially impact efficacy analysis and exclude a subject from PP population are listed in Appendix 5. Refer to the study protocol deviation specification for more information.

The following protocol deviation summaries will be provided:

- Number and percentage of subjects with a major protocol deviation by type of deviation (Analysis population: ITT)
- Number and percentage of subjects with a major protocol deviation resulting in exclusion of subjects from PP analysis by type of deviation (Analysis population: ITT)

A by-subject listing of protocol deviations will be provided.

4.4 Analysis Populations

The following analysis populations will be used to analyze the data.

Intent-to-Treat Population (ITT):

The ITT population will consist of all randomized subjects.

Per Protocol Population (PP):

The PP population will comprise all subjects in the ITT population who have no major protocol deviations that would have a significant effect on the efficacy of the study treatment. The PP population will be finalized prior to the final database lock.

Safety Population (SAF):

The safety (SAF) population will comprise all subjects in ITT population who receive at least one dose of study drug.

PK Analysis Population (PKAP):

The PK analysis population will include all subjects in the SAF population who provide at least one post-baseline evaluable drug concentration value.

The efficacy summaries and analyses will be based on the ITT population, which is based upon the Intention-to-Treat (ITT) principle. In the event that a subject is allocated the incorrect study treatment as per the study randomization list, subjects will be summarized and analyzed ‘as randomized’ (i.e., by randomized treatment group). In the event that a subject is stratified incorrectly, ‘randomized stratum’ will be used rather than ‘actual stratum’.

For the primary and selected secondary efficacy endpoints, a sensitivity analysis will be performed on the PP population to assess the robustness of the study conclusions to the choice of analysis population. Subjects will be included in the analysis according to the treatment ‘as randomized’.

The safety summaries and analyses will be based on the SAF population. Randomized subjects will only be excluded if there is clear, documented evidence that the subject did not receive any study drug injection. In the event that a subject is allocated the incorrect study treatment as per the study randomization list, subjects will be summarized and analyzed ‘as treated’ (i.e., by allocated treatment group).

Upon database release, protocol deviation and analysis population outputs will be produced and will be reviewed by Sponsor. An analysis population classification meeting will be arranged to discuss the outputs and to decide which subjects and/or subject data will be excluded from certain analyses. Decisions made regarding the exclusion of subjects and/or subject data from analyses will be made prior to database lock and unblinding and will be documented and approved by Sponsor.

The following analysis population summaries will be provided:

- The number and percentage of subjects in each study population will be presented by study treatment group including total (Analysis population: ITT).

A by-subject listing of analysis population details will be provided. This listing will be presented by treatment group and will include: subject identifier, inclusion/exclusion flag for each population and reason for exclusion from each population. All subjects screened will appear on this listing.

The following derived and computed variables will be produced:

Variable Description	Computation Methods, Notes, or Equation(s)
Flag of ITT subjects	'Y' if subjects randomized into the study; otherwise 'N'
Flag of SAF subjects	'Y' if subjects in ITT and date and/or time of the first dose injection on Study Drug Administration form is non-missing; otherwise 'N'
Flag of PP subjects	'Y' if subjects in ITT who complete 24-week Treatment Period with the exception of major protocol violators who have significant effect on the efficacy; otherwise 'N'

4.5 Demographic and Other Baseline Characteristics

Descriptive summaries of demographic and other baseline conditions will include the following:

- Demographics - age, gender, race, ethnicity, height, weight, and body mass index (BMI)
- Medical history
- Previous and concomitant medications

4.5.1 Demographics and baseline characteristics

The following demographic and baseline characteristics will be summarized by descriptive statistics (Analysis population: ITT):

- Age at time of informed consent (in years, as a continuous variable)
- Age categorization (≤ 65 , > 65 years)
- Gender (Male, Female)
- Race (White, Black or African American, Asian, American Indian or Alaska Native, Hawaiian Native or Other Pacific Islander, Other)
- Ethnicity (Hispanic or Latino, Not Hispanic or Latino)
- Weight at baseline (in kilograms)
- Height at screening (in centimeters)
- BMI (kg/m^2) calculated using weight and height at screening
 $\text{BMI} (\text{kg}/\text{m}^2) = \text{weight} (\text{kg}) / \text{height} (\text{m})^2$
- Baseline EASI
- Baseline IGA
- Baseline AD involvement of BSA (as a continuous variable)
- Baseline average and peak pruritus NRS (weekly average during the 7 days prior to day 1, as a continuous variable)
- Number of days with severe pruritus (based on PCS) during the 7 days prior to day 1 (≥ 3 , 3, 4, 5, 6, 7)
- Intrinsic or extrinsic AD (refer to Appendix 6)
- Total SCORAD

Stratification factor includes IGA (3 or 4). A summary table for the stratification factor will be provided to show if any discrepancies between what was reported through Interactive Voice Response System (IVRS)/Interactive Web Response System (IWRS) versus eCRF data (at baseline visit).

By-subject listings of demographic data and other baseline characteristics (as summarized above) will be provided.

